Ocular surface complications in primary open-angle glaucoma

Occurrence of the ocular surface complications in primary open-angle glaucoma patients
on treatment with IOP lowering eye drops

Project protocol, 04.09.2021.

Introduction:

Glaucoma is a chronic progressive optic neuropathy characterized by retinal ganglion cell death and optic nerve fiber layer loss that can cause progressive deterioration of the peripheral vision, and if left untreated, can lead to severe visual impairment and even blindness (Weinreb, Aung, & Medeiros, 2014). Elevated intraocular pressure (IOP) is the most consistent risk factor for developing glaucoma, and lowering it is the only recognized treatment method (Boland et al., 2013). Topical IOP-lowering eye drops are often used as the first line of treatment to reduce the intraocular pressure and prevent damage to the optic nerve; however, recent research indicates an association between topical treatment and ocular surface disease (OSD) (Zhang, Vadoothker, Munir, & Saeedi, 2019).

The prevalence of OSD in patients with glaucoma varies from 22% to 78%, depending on the specific test used (Baudouin et al., 2013; Fechtner et al., 2010; Leung, Medeiros, & Weinreb, 2008). Research agrees that glaucoma and ocular surface disease co-exist, and OSD often worsens with age, duration of the treatment, and a number of topical IOP lowering eye drops with and without preservatives (Baudouin et al., 2013; Stewart, Stewart, & Nelson, 2011). Dryness, fatigue, burning, variable visual acuity, and photophobia are the most common symptoms of OSD and can affect a patient's ability to work and quality of life (Leung et al., 2008; Zhang et al., 2019). Schwartz et al. demonstrated that 23 to 59% of patients are not adherent to prescribed therapy with topical IOP lowering medication, but it is unclear whether this is related to OSD (Schwartz & Quigley, 2008). A study by Boso et al. that investigated the impact of the OSD treatment in glaucoma patients (Boso, Gasperi, Fernandes, Costa, & Alves, 2020) showed that short-term treatment could improve signs and symptoms of OSD. A better understanding of the cause-effect relationship between OSD and glaucoma treatment with IOP-lowering eye drops may help individualize treatment options for patients in agreement with personalized medicine.

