3. In a sample of patients with POAG, who have been on treatment with IOP lowering eye drops for at least three months, the frequency of signs of OSD, defined as hyperosmolarity, reduced NIKBUT, ocular surface staining, or reduced Schirmer 1 test is modified by the active pharmacological substance in the IOP-lowering eye drops.
4. In a sample of patients with POAG, who have been on treatment with IOP lowering eye drops for at least three months, the frequency of symptoms of OSD, defined as OSDI index ≥ 13 or SPEED II values >5 , is modified by the active pharmacological substance in the IOP-lowering eye drops.
5. In a sample of patients with POAG, who have been on treatment with IOP lowering eye drops for at least three months, the frequency of signs of OSD, defined as hyperosmolarity, reduced NIKBUT, ocular surface staining, or reduced Schirmer 1 test is related to the duration of the treatment with an IOP-lowering eye drop of a specific pharmacological category (prostaglandin analogs, beta-blocker, carbohydrase inhibitor or alfa-2-agonist).
6. In a sample of patients with POAG, who have been on treatment with IOP lowering eye drops for at least three months, the frequency of symptoms of OSD, defined as OSDI index ≥ 13 or SPEED II values >5 , is related to the duration of the treatment with an IOP-lowering eye drop of a specific pharmacological category (prostaglandin analogs, beta-blocker, carbohydrase inhibitor or alfa-2-agonist).

The secondary objective of this study is to investigate a relationship between compliance and signs and symptoms of the ocular surface disease.

The secondary objective of the study was based on the following research questions:

1. Is the occurrence of signs and symptoms of OSD in patients with POAG related to self-reported compliance to the treatment with the IOP lowering eye drops?
2. Is the occurrence of signs and symptoms of OSD in patients with POAG independently related to self-reported compliance to the treatment with the IOP lowering eye drops?

Based on these research questions, the following hypotheses were formulated:

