1. In a sample of patients with POAG who have been on treatment with IOP lowering eye drops for at least three months, the frequency of signs of OSD, defined as hyperosmolarity, reduced NIKBUT, ocular surface staining, or reduced Schirmer 1 test, is different in patients with self-reported poor compliance, defined as single dose skipped or forgotten more than once a week (Robin & Grover, 2011), compared with patients with good self-reported compliance.
2. In a sample of patients with POAG who have been on treatment with IOP lowering eye drops for at least three months, the frequency of symptoms of OSD, defined as OSDI index ≥ 13 or SPEED II values >5 , is different in patients with self-reported poor compliance, defined as single dose skipped or forgotten more than once a week, compared with patients with good self-reported compliance.

3. In a sample of patients with POAG who have been on treatment with IOP lowering eye drops for at least three months, the frequency of signs of OSD, defined as hyperosmolarity, reduced NIKBUT, ocular surface staining, or reduced Schirmer 1 test, is different in patients with self-reported poor compliance, defined as single dose skipped or forgotten more than once a week, compared with patients with good self-reported compliance, when adjusted for preservatives, pharmacological substance, and duration of treatment.
4. In a sample of patients with POAG who have been on treatment with IOP lowering eye drops for at least three months, the frequency of symptoms of OSD, defined as OSDI index ≥ 13 or SPEED II values >5 , is different in patients with self-reported poor compliance, defined as single dose skipped or forgotten more than once a week, compared with patients with good self-reported compliance, when adjusted for preservatives, pharmacological substance, and duration of treatment.

The results are expected to improve the understanding of the connection between glaucoma treatment with IOP-lowering eye drops and ocular surface disease. Acknowledgment of the problem may help to individualize treatment options for patients in agreement with personalized medicine. This could consequentially lead to the general improvement of patient life quality and treatment compliance that could also positively affect glaucoma treatment outcomes.

Study design:

This is a cross-sectional study with six months prospective data collection.

Study sample:

The target population is patients on topical treatment for POAG.

Study population:

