This study is a sub-study of an “Ocular Surface and glaucoma. A randomized study of IOP reducing eye drops versus surgical intervention” study (REK no. 253485). Invited to participate in the study are men and women between 50 and 75 years of age with early POAG, diagnosed in agreement with the European guidelines for glaucoma diagnoses and staging of the disease, with MD loss of less than 5 dB on visual fields and with a clinically significant cataract eligible for surgery, who come for a routine glaucoma follow-up examination and a presurgical assessment for cataract extraction at the ophthalmology practice of Ifocus Øyeklinikk in Haugesund, Norway, in the period between August 2021 and February 2022.

Exclusion criteria:

- Recent changes (<3 months) in the treatment with topical IOP-lowering medications (i.e., active pharmacological substance, dosage, preservatives) based on the patient medical journals.
- Use of more than one IOP-lowering eyedrops with different active pharmacological substances based on the patient medical journals.
- Self-reported OSD comorbidity defined as an autoimmune or inflammatory disease, such as Sjogren’s syndrome or Rheumatoid Arthritis (RA), or any other systemic disease that can directly affect the ocular surface.
- Conditions that may confound the results of the study:
 - Self-reported acute or chronic diseases such as connective tissue disease, clinically significant atopic disease, diabetes type 1 and 2, immunocompromised, or any other such condition.
 - Manifest corneal disease, dystrophy, or scarring based on the clinical exam.
 - Corneal ectasia based on the clinical exam.
 - Lid deformities based on the clinical exam.

- Recent intra- or extra-ocular surgery based on the patient medical journals.
- Previous refractive procedures like LASIK, LASEK, or radial keratotomy based on the patient medical journals.
- A previous corneal transplant, DSAEK, lamellar keratoplasty, or similar procedure based on the patient medical journals.

Recruitment:

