Active pharmacological substance is an ingredient used in a finished pharmaceutical product, intended to provide pharmacological activity or to otherwise have a direct effect in the diagnosis, cure, treatment, or prevention of disease. Operationally, the active pharmacological substance is defined as any of the following substances in the specification of the prescribed eye drops during the period of 3 months before inclusion into the study: prostaglandin analogs, beta-blocker, carbohydrase inhibitor, or alfa-2-agonist. The active pharmacological substance used by the patients will be known from the patient history and will be noted on a nominal scale (1= prostaglandin analogs, 2=beta-blocker, 3=carbohydrase inhibitor, 4= alfa-2-agonist).

The duration of the treatment is defined as the period in which the patient has been treated with the same pharmacological substance. Operationally, it is defined as information about the duration of the treatment collected from the medical records and registered on a numerical scale with the whole number of months of use.

Self-reported compliance is defined as an act complying or adhering to requirements (prescribed treatment). Operationally, it is defined as self-reported adherence to taking drops in agreement with the prescription measured by means of a simple interview question of how often one may skip a dose (0: Less than once or twice a month; 1: Once or twice a month; 2: Approximately once a week; 3: More than once a week). It will be registered on an ordinal scale.

Other variables:

Age will be registered as the whole number of years on a numerical scale.

Sex will be registered as female=1 and male=0 on a dichotomous scale.

Methods:

Recruitment:

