
Analyses:

The results of the comprehensive tear film evaluation will be recorded in the patient journal system (Infodoc Plenario) used at the Ifocus Øyeklinikk, Haugesund, Norway. The data collected with the Oculus Keratograph 5M by OCULUS, Inc. will be stored in a separate database called Oculus Patient Data Management. Once measurements are performed, data related to the study will be transferred from the patient journal to a data registration form (Appendix 4). The names of the patients will be replaced with ID numbers. All data will be transferred to and organized in a database (Excel, Microsoft Inc.). To identify empty cells or unrealistic values, an algorithm in Excel will flag the cells in question. A quality-assured version of the database will constitute the basis for statistical analyses. For variables measured on a numerical scale, these summaries will include the sample size, as well as the mean, standard deviation, median, minimum, and maximum. For variables measured on a categorical scale, summaries will provide the number and percentage of subjects who provided each score. Preliminary considerations of the data will include the investigation as to whether any transformation (i.e., logarithmic) should be applied prior to the statistical analyses. For categorical data, the sparseness of the data across categories will be considered, and the combination of categories prior to statistical analysis will be applied where deemed appropriate. For variables measured on a continuous scale, the statistical significance of the difference

between groups will be investigated using an Analysis of Variance (ANOVA) with appropriate post-hoc testing. For variables measured on an ordinal categorical scale, the Kruskal-Wallis signed-rank test will be employed. Questionnaire data will be analyzed using current standards. The statistical analyses will be performed using SPSS version 24. All statistical tests of hypotheses will employ a level of significance of $\alpha=0.05$. Odds ratios with 95% confidence intervals may also be used.

Project management and organization:

Principal investigator: [name]

Project manager: [name]

Resources, equipment, and physical facilities:

All equipment is available in the ophthalmic practice Ifocus Øyeklinikk in Haugesund, Norway, where the study will take place:

- The TearLab Osmolality System by TearLab Corporations.
- The Oculus Keratograph 5M by OCULUS, Inc.

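### Age is named as worsening OSD and is recorded, but it enters no stated inferential analysis, so the duration results and the 'independent' compliance result may carry an age effect

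*Protocol*

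**What the plan says.** The Introduction summarises earlier research in these words: "OSD often worsens with age, duration of the treatment, and a number of topical IOP lowering eye drops". Age therefore stands first in the list, next to the exposure studied in main hypotheses 5 and 6.

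Study population invites "men and women between 50 and 75 years of age with early POAG", a span of 25 years. The Variables section states: "Age will be registered as the whole number of years on a numerical scale". That line is under Other variables, not among the predictors.

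Main hypotheses 5 and 6 propose that the frequency of signs or symptoms "is related to the duration of the treatment with an IOP-lowering eye drop of a specific pharmacological category". They name no adjustment covariate.

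The second secondary research question asks whether OSD is "independently related to self-reported compliance to the treatment with the IOP lowering eye drops". Secondary hypotheses 3 and 4 answer it with a listed set: "when adjusted for preservatives, pharmacological substance, and duration of treatment". Age is not in the list.

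The Analyses section says that for continuous variables the difference "between groups will be investigated using an Analysis of Variance (ANOVA) with appropriate post-hoc testing". Ordinal variables get a Kruskal-Wallis test, and odds ratios are optional. No covariate is attached to any of these. The only use of age that follows from the text is in the descriptive summaries of numerical variables.

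**The concern.** The Introduction gives three drivers of OSD: age, duration of treatment and number of drops. Duration is a predictor and is in the adjustment set. The number of drops is handled by excluding patients who use more than one active substance. Age is only limited to the entry range.

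If older patients in this sample have been longer on their current substance, an association between months of treatment and OSD under main hypotheses 5 and 6 cannot be told apart from an association with age. For compliance, a result presented as independent would leave out a risk factor that the protocol names itself. The claim at stake is that duration or compliance, rather than age, goes with OSD.

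**Working it through.** The protocol gives no effect size, power or sample-size calculation, and 30 patients is a feasibility number. There is thus no stated figure to reproduce. The check has three steps.

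**1. Where age is used.**

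| Place in the protocol | Covariates named | Age? |
|---|---|---|
| Main hypotheses 1-4 | none | no |
| Main hypotheses 5-6 (duration within a substance category) | none | no |
| Secondary hypotheses 1-2 (compliance, crude) | none | no |
| Secondary hypotheses 3-4 (compliance, adjusted) | preservative, substance, duration | no |
| Analyses: ANOVA, Kruskal-Wallis, optional odds ratios | none | no |
| Analyses: summaries of numerical variables | not applicable | yes, descriptive only |

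**2. How large an age effect could be.**

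From the protocol: N = 30, ages 50 to 75, alpha 0.05 (taken as two-sided). Assumed, because the protocol gives neither: an odds ratio of OSD per decade of age of 1.5, 2 or 3, and an age-duration correlation r of 0 to 0.6. Also assumed: age uniform over the entry range, and OSD present in about half the patients.

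Model: logit P(OSD) = ln(OR) × (age − 62.5)/10. Duration has no true effect. The spurious odds ratio comes from a simulated sample of 300,000. The false-positive rate comes from 3,000 simulated studies of 30 patients, comparing duration between patients with and without OSD.

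| Age OR per decade | r | Spurious OR per SD of duration | False-positive rate, crude | False-positive rate, age-adjusted |
|---|---|---|---|---|
| 1.5 | 0 | 1.01 | 0.050 | 0.052 |
| 1.5 | 0.2 | 1.05 | 0.052 | 0.051 |
| 1.5 | 0.4 | 1.12 | 0.061 | 0.057 |
| 1.5 | 0.6 | 1.18 | 0.072 | 0.048 |
| 2 | 0 | 1.00 | 0.055 | 0.054 |
| 2 | 0.2 | 1.10 | 0.060 | 0.055 |
| 2 | 0.4 | 1.21 | 0.090 | 0.056 |
| 2 | 0.6 | 1.33 | 0.116 | 0.050 |
| 3 | 0 | 1.00 | 0.043 | 0.046 |
| 3 | 0.2 | 1.16 | 0.069 | 0.051 |
| 3 | 0.4 | 1.33 | 0.105 | 0.053 |
| 3 | 0.6 | 1.56 | 0.200 | 0.052 |

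With age in the model, the odds ratio for duration lies between 0.99 and 1.01 in every setting.

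**3. Whether 30 patients can carry one more covariate.**

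Parameters in the listed set for secondary hypotheses 3-4: compliance 1 + preservative 1 + substance 3 (four classes) + duration 1 = 6.

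- Adding age: 6 + 1 = 7.
- Adding age, with substance reduced to two levels as a covariate: 1 + 1 + 1 + 1 + 1 = 5.

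The Introduction gives OSD prevalence as 22% to 78%. At either end the smaller outcome class has 30 × 0.22 = 6.6 patients; at 50% it has 15.

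| Parameters | Patients per parameter at 22% or 78% | Patients per parameter at 50% |
|---|---|---|
| 6 (as listed) | 6.6/6 = 1.1 | 15/6 = 2.5 |
| 7 (age added) | 6.6/7 = 0.9 | 15/7 = 2.1 |
| 5 (age added, two-level substance) | 6.6/5 = 1.3 | 15/5 = 3.0 |

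All three are sparse. The five-parameter set is less overloaded than the one listed.

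**The case against.** Several stronger readings are tempting, and the protocol does not support them.

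- A reader might infer that age is not used at all. It would appear in the descriptive summaries; what is missing is any stated inferential use.
- A reader might infer that the duration results do carry an age effect. No section says that older patients have been treated longer. Duration is defined as time on the same substance, so it restarts when the substance changes, and entry is limited to early disease and one active substance. Both could weaken the link with age. At zero correlation there is no bias, and with an age odds ratio of 1.5 per decade the false-positive rate reaches only 0.072.
- A reader might infer the same for compliance. Nothing in the protocol links age to compliance, so bias there is possible but not shown.
- A reader might express the bias as a share of outcome variance or in standard deviations. The hypotheses concern the frequency of signs or symptoms past a cut-off, so figures for a continuous score do not fit.

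It can also be said that covariates are commonly settled in a statistical analysis plan, which is not shown here. For main hypotheses 5 and 6 that has weight, since they fix no set. It has little for secondary hypotheses 3 and 4, where the adjustment set is part of the hypothesis.

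Finally, a single model with substance reduced to two classes throughout would remove the substance question of main hypotheses 3 and 4 and the category-specific question of 5 and 6. That objection stands, and the fix below respects it.

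**Conclusion.** The point holds in a limited form. The protocol states that "OSD often worsens with age, duration of the treatment" and records age, but leaves it out of the covariate set meant to answer the independence question and names no covariate for duration. Following the text as written, the duration results may carry an age effect, and the adjusted compliance result may too. The case is stronger for duration.

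The size is unknown. Under the assumed values above, with correlations of 0.2 to 0.6, the spurious odds ratio per SD of duration runs from 1.05 to 1.56 and the false-positive rate from 0.05 to 0.20. These ranges rest wholly on the assumed age effect and correlation. The removal of the bias by adjustment rests on the age effect being close to linear on the log-odds scale. This is a worthwhile improvement at low cost; it does not show that the planned results would be wrong.

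**What to change.** - Add age (years, linear) to the covariates of secondary hypotheses 3 and 4.
- Report main hypotheses 5 and 6 with age adjustment, beside the crude result.
- Name the model, since the Analyses section names none that yields an adjusted estimate. A patient-level model suited to sparse binary data would serve, for example penalised logistic regression. Label its results exploratory.
- Keep the four-class substance comparison in main hypotheses 3 and 4 and the category-specific duration question in 5 and 6. Reduce substance to two levels only where it is an adjustment covariate in secondary hypotheses 3 and 4.

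The cost is a few sentences and no new data. The two-level substance covariate adjusts less finely for substance. Without that reduction, the set grows from 6 to 7 parameters. With about 7 patients in the smaller outcome class at 22% or 78% prevalence, the adjusted estimates will be imprecise either way, and the report should say so.

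### The single-substance restriction counts eyedrops, so one bottle with two active substances is not excluded, yet substance and duration are recorded as if each patient had only one

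*Protocol*

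**What the plan says.** Four places in the protocol bear on this.

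- **Exclusion criteria.** The restriction on multiple medication is "Use of more than one IOP-lowering eyedrops with different active pharmacological substances based on the patient medical journals".
- **Predictor variables, active pharmacological substance.** The operational definition is that "the active pharmacological substance is defined as any of the following substances in the specification of the prescribed eye drops". It is recorded on one nominal scale: "1= prostaglandin analogs, 2=beta-blocker, 3=carbohydrase inhibitor, 4= alfa-2-agonist". There is no code for a combination.
- **Predictor variables, duration of the treatment.** Duration is "the period in which the patient has been treated with the same pharmacological substance", in whole months.
- **Research objectives and significance.** Main hypotheses 3 and 4 ask whether the frequency of signs or symptoms "is modified by the active pharmacological substance in the IOP-lowering eye drops". Main hypotheses 5 and 6 ask whether that frequency "is related to the duration of the treatment with an IOP-lowering eye drop of a specific pharmacological category". Secondary hypotheses 3 and 4 compare poor with good compliance after adjustment for preservatives, substance and duration.

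The protocol does not mention products that combine two substances in one bottle, either to exclude them or to code them.

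**The concern.** Main hypotheses 3-6 make sense only if each patient is exposed to one pharmacological class. The exclusion criterion is the one place where the protocol tries to secure this, and it does so by number of eyedrops. The recording scale and the duration definition assume that it has succeeded.

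If a patient on a two-substance bottle enters, the whole exposure is credited to one class, and nothing in the protocol says which. A comparison of classes would then no longer be a comparison of single substances. Duration within a class would depend on which component the clock is started for. The same two variables are covariates in the adjusted compliance hypotheses, so the ambiguity carries over to them. In all, four of the six main hypotheses and two of the four secondary ones rely on one substance per patient. With 30 subjects spread over four classes, a few arbitrary codes could matter in a thin class.

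**Working it through.** The protocol states no figure on this point. The sample of 30 is justified by feasibility, with no effect size or power, so there is nothing to reproduce. The check is mainly a reading of the text.

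**Step 1: who is excluded.** The criterion joins two conditions: (a) more than one eyedrop and (b) different active substances.

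| Patient | (a) | (b) | Excluded? |
|---|---|---|---|
| One bottle, one substance | no | no | no |
| Two bottles, different substances | yes | yes | yes |
| One bottle, two substances | no | yes | **no** |

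**Step 2: how the third patient is coded.** The definition accepts any listed class found in the specification of the drops. A bottle with substances from two different listed classes therefore satisfies two of the four codes, on a scale that takes one. No order of precedence is given.

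**Step 3: how duration is recorded.** Suppose the patient used component A alone for some time and later moved to a bottle with A and B. Time on A is then longer than time on B, and both meet the definition. The exclusion of treatment changes within the last three months does not prevent this, because an older change is allowed.

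**Step 4: whether another section closes the gap.** The Analyses section allows categories to be combined when data are sparse. That merges thin categories; it does not place a patient who belongs to two. No other section addresses the case.

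**Step 5: which hypotheses are touched.** Substance or duration enters main hypotheses 3-6 and secondary hypotheses 3-4. Main hypotheses 1-2 (preservative) and secondary hypotheses 1-2 (unadjusted compliance) use neither and are not affected.

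**Step 6: how many patients.** The share f of single-bottle, two-substance users is not in the documents and is assumed. With N = 30 (Recruitment section), the expected number is 30 × f. Treating patients as independent, the chance of at least one is 1 − (1 − f)^30.

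| Assumed f | Expected number | P(at least one) |
|---|---|---|
| 0% | 0 | 0 |
| 5% | 1.5 | 0.785 |
| 10% | 3.0 | 0.958 |
| 20% | 6.0 | 0.999 |

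**Step 7: why the destination code matters.** The documents give no split by class. As an illustration only, suppose 20 subjects are coded to one class and 10 to the other three together. Three combination users would be 3/20 = 15% of the large class, or 3/10 = 30% of the smaller ones. Six would be 6/20 = 30% or 6/10 = 60%. With f = 0 every figure is zero. The range is therefore 0% to 60%, and the upper end requires both the highest assumed share and every such patient being coded into the smaller classes.

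**The case against.** **The intent is clear.** The criterion's reference to different substances, the four single-class codes and the singular in the duration definition all point to one substance per patient. The study runs at one clinic, one observer does the examinations, and substance is read from the clinic's own journals, so sites cannot read the rule differently. This stands as a reason to call the point a drafting gap that is easily closed. It does not remove the gap: excluding these patients by intent would be an unwritten rule that a reader could not verify.

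**Enrolment is not certain.** Participants come from those who consented to the parent randomized study, whose criteria are not shown and may restrict treatment. Exclusion criteria also do not oblige anyone to enrol a patient. This stands, and the consequence can only be stated conditionally.

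**The statistical analysis plan may handle it.** A coding rule could be set there. Eligibility could not, and the recording scale and the duration definition are already fixed in the protocol in a form that does not suit everyone the criterion admits.

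**The study is small anyway.** Thirty subjects over four classes make main hypotheses 3-6 weakly informative with or without a few such patients. This is fair, and no change in any conclusion can be shown. A small study is nevertheless the one in which a few arbitrary codes weigh most.

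**Stronger readings.** A reader might infer that these patients differ systematically in ocular surface disease, because the Introduction says that it worsens with the number of drops. That statement concerns the number of drops, and a combined product is one drop, so it does not support the inference. A reader might also infer that such a patient fits none of the four codes; under the operational definition the patient fits two.

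**Conclusion.** The point holds in conditional form. As written, the criterion admits a patient on one bottle with two active substances. The coding scale then offers that patient two valid codes on a one-choice scale, and the duration definition can give two values. If any such patient is enrolled, main hypotheses 3-6 and the substance and duration adjustment in secondary hypotheses 3-4 can be contaminated.

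The size is unknown. The expected number is 0 to 6 of 30 for assumed shares of 0% to 20%, and the effect depends on the class to which the patients are coded. One might infer that a third or more of the smaller classes would be miscoded. That requires an assumed share, an assumed class split and an assumed direction of coding all at once, and the documents support none of the three. Nor do they support saying that the hypotheses are contaminated, since the share may be zero.

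The textual finding rests on no assumption beyond reading the criterion literally. It deserves correction because the stated rules do not fit one another and the correction is cheap.

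**What to change.** Reconcile the exclusion criterion, the substance and duration definitions under Predictor variables, and main hypotheses 3-6. Two routes would do this; the choice is the sponsor's.

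1. **Word the restriction by substance.** State the exclusion by number of active IOP-lowering substances, whether in separate bottles or in one combined product. The four codes and the duration definition then fit every enrolled patient. The cost is one sentence and somewhat slower recruitment: 0 to 6 candidates per 30 under the shares assumed above.
2. **Keep these patients and code them.** Add a combination code and leave those patients out of main hypotheses 3-6. Then state how their substance and their duration enter secondary hypotheses 3-4. The last step is needed because a new code alone does not define duration, and both variables are covariates there. The cost is one code on the data registration form, a few sentences, and a few fewer analysable patients for main hypotheses 3-6. The patients remain available for the descriptive question, the preservative hypotheses and the unadjusted compliance hypotheses.

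If enrolment has already begun, the second route avoids making recruited patients ineligible afterwards. Under either route, the report should give the number of patients on combined products who were excluded or coded as such.
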